**Annex 3.3: Morisky 8-item questionnaire on adherence to treatment**

**Questionnaire in relation to your treatment**

(Mark only one response per question)

	Yes	No
1. Do you ever forget to take your treatment?		
2. Sometimes some persons do not take their medicinal products for reasons other than forgetfulness. By thinking about the last two weeks, have there been any days when you did not take your treatment?		
3. Has it ever happened for you to reduce the dose or to discontinue taking your treatment without telling your doctor because you feel less well by taking it?		
4. When you travel or when you leave the house, does it happen that you forget to take your treatment with you?		
5. Have you taken your treatment yesterday?		
6. When you experience much less or even not at all your symptoms, does it happen sometimes for you to stop taking your treatment?		
7. Does the fact of having to take your treatment everyday represent a real inconvenience for certain patients? The fact of having to take your treatment every day represents a real inconvenience for certain patients. Does it sometimes happen for each to be upset by the fact of having to adhere to your treatment?		
8. Does it happen that you have difficulty in remembering to take your treatment?  Never/Rarely  From time to time  Sometimes  Regularly  All the time		

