Hematologic, cytogenetic and molecular tests performed for monitoring of response to treatment (type and frequency of monitoring, results of tests)	Evaluation end point	Follow-up visit
Compliance with treatment with bosutinib (Morisky Questionnaire) *	Evaluation end point	Follow-up visit
Quality of life (FACT-leu_v4)*	Baseline characteristics Evaluation end point	Inclusion visit Follow-up visit
Patient status and date of last news (date of death if applicable)	Evaluation end point	End of study
Last hematological, cytogenetic and molecular responses known	Evaluation end point	End of study

Status of treatment with bosutinib	Evaluation end point	End of study
------------------------------------	----------------------	--------------

\* Morisky medication adherence scale and fact leu self-questionnaire are intended solely for patients under treatment with bosutinib.

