#### 9.4.1.5. Measurement of compliance with treatment

Compliance with treatment will be evaluated directly in patients using a Morisky standardized validated questionnaire (Annex 3). This generic questionnaire on evaluation of adherence with treatment consists of 7 questions for which the rating scale is 0 for “YES”

(reflection of poor compliance) and 1 for “NO” (reflection of good compliance), and an 8th question with 5 response modalities ranging from “never/rarely” to “all of the time” which makes it possible to qualify the degree of agreement [23].

This questionnaire will be returned by the patient to the participating doctor at the end of the visit. All adverse events identified by the participating doctor via these questionnaires (if the patient has ticked YES to questions **3, 6**) must be reported in the study database and be reported through the Pfizer Pharmacovigilance department (*see section 11 Erreur ! Source du renvoi introuvable.*

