#### **Adherence to treatment (Morisky Questionnaire).**

The MMAS-8 rating scale consists of eight items with a “Yes” = 0 and “No” = 1 rating system for the first seven items and a 5-point response for the last item. Items will be added in order to obtain a score.

- The score will be described continuously and categorically (0 = high adherence, 1-2 = average adherence,  $\geq 3$  = low adherence) at each measurement time.

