#### **Describing treatment modalities for bosutinib under real life conditions of use**

- Dosage: mean dosage prescribed at time of initiation and average dosage during treatment.
- Change to dose and reasons: percent of patients with dose reduction/percent of patients with a dose increase and if applicable, description of the reason .
- Maintenance of dose intensity and relative dose intensity (defined as the result of the ratio of the dose received over the expected dose): percent of patients with a dose intensity/relative dose intensity maintained over time and at different measurement times.
- Temporary discontinuation of treatment: percent of patients with temporary discontinuation of treatment and description of the reason; cumulative duration of temporary discontinuations.

- Permanent discontinuation of treatment: percent of patients with a permanent discontinuation of treatment and description of reason for discontinuation.
- Duration of treatment: duration of initiation up to discontinuation of treatment will be calculated for all causes of discontinuation combined and by cause of discontinuation (Kaplan-Meier survival curves).

**Cumulative response to treatment (hematological, cytogenetic and molecular results) and duration up to response and response time**

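### Once the Morisky scoring is put right, item 2 still counts a doctor-ordered bosutinib stop in the last 14 days as a lapse, moving an otherwise fully adherent patient who has resumed from high to average adherence

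*Protocol*

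**What the plan says.** Item 2 of the form in Annex 3.3 opens with "Sometimes some persons do not take their medicinal products for reasons other than forgetfulness" and then asks "By thinking about the last two weeks, have there been any days when you did not take your treatment". Item 5 asks "Have you taken your treatment yesterday". Neither sets aside days on which the doctor had stopped the drug. Item 3 does so in effect, because it is limited to reducing or stopping "without telling your doctor because you feel less well by taking it".

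Section 9.4.1.5 treats a Yes on items 1–7 as a sign of poor compliance. Section 9.7.3 codes Yes as 0 and No as 1, adds the items, and labels 0 as high, 1–2 as average and 3 or more as low. It adds that "The score will be described continuously and categorically" at each measurement time. The footnote to section 9.3 says that the Morisky and FACT-leu forms "are intended solely for patients under treatment with bosutinib", and section 9.4.1 says the same. Table 4 schedules the Morisky form at all 12 follow-up visits, M3 to M36.

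The treatment-modalities part of section 9.7.3 also describes interruptions: "percent of patients with temporary discontinuation of treatment and description of the reason; cumulative duration of temporary discontinuations".

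**The concern.** Temporary discontinuation is an expected course in this study. Sections 7.4 and 8 name it among the ways adverse events are managed, and section 9.7.3 reports it. One prescribed stop can therefore appear twice: as a managed interruption in one table and as a lapse by the patient in the adherence table. An analyst who scores the form mechanically would not see the overlap. At stake is whether the share of patients in the highest adherence category can be read as the patients' own behaviour.

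**Working it through.** **Inputs.** Item wording comes from Annex 3.3, and coding and cut-offs from sections 9.4.1.5 and 9.7.3. Item 8 has no numeric code in the protocol.

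Take three patients who are otherwise perfect and answer literally (items 1–7, Y/N):

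- A, continuous taker: N N N N Y N N
- B, doctor-ordered stop within the last 14 days, resumed before yesterday: N Y N N Y N N
- C, doctor-ordered stop still in force yesterday: N Y N N N N N

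**Step 1: the scoring as written.** With Yes = 0 and No = 1, items 1–7 sum to A = 6, B = 5, C = 6. Adding 0, 1 or 4 for item 8 (an assumed range) leaves all three at 3 or more, so all are *low*, including the perfect taker. The rule also rewards a Yes on item 2: the smallest possible sum of items 1–7 is 0 with item 2 = Yes and 1 with item 2 = No. Coding and categories therefore cannot both stand. That is a separate fault, and it has to be settled first.

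**Step 2: the apparently intended direction.** Count lapses: Yes = 1 on items 1–4, 6 and 7; No = 1 on item 5; item 8 *never/rarely* taken as 0. Of the variants tried, this is the only one that the 0 / 1–2 / ≥3 cut-offs fit.

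| Patient | Lapse count | Category | If the prescribed stop were exempt |
|---|---|---|---|
| A | 0 | high | 0, high |
| B | 1 | average | 0, high |
| C | 2 | average | 0, high |

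**Step 3: other directions.**

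- Keep No = 1 as good, so that a higher sum means better adherence. With item 5 unreversed the sums are A 6, B 5, C 6. With item 5 reversed they are A 7, B 6, C 5. B loses a point either way. C loses none while item 5 is unreversed, because its miscoding offsets item 2. The protocol gives no cut-offs for this direction, so no category follows.
- Code Yes = 1 without reversing item 5. The counts are A 1, B 2, C 1, all *average*, so even the perfect taker is not *high*.

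**Step 4: how many forms.** The protocol gives no interruption rate. Assume a share p of patients has one interruption of L days, placed at random in the 91 days (about three months) before a visit.

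Patients already resumed (type B), share = p × 14/91:

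- p = 0.15: 0.15 × 14/91 = 2.3%
- p = 0.30: 0.30 × 14/91 = 4.6%
- p = 0.40: 0.40 × 14/91 = 6.2%

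If patients still interrupted (type C) also complete the form, share = p × (L + 14)/91:

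- p = 0.15, L = 7: 0.15 × 21/91 = 3.5%
- p = 0.30, L = 14: 0.30 × 28/91 = 9.2%
- p = 0.40, L = 21: 0.40 × 35/91 = 15.4%

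If instead 30% have one interruption at some time over the 12 quarters of follow-up, resumed patients affect 0.30 × 14/91 ÷ 12 = 0.4% of forms at a visit.

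**The case against.** The strongest reply is that this is a matter for the SAP. Section 9.7.3 ends by deferring detail on secondary objectives to it, the SAP is not at hand, and a rule for handling particular forms is ordinary SAP content. That is partly right: the SAP could carry the remedy. But the form's wording, who completes it and its scoring at each visit are fixed in the protocol, and together they produce the overlap unless someone acts on it.

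A second reply is that patients may not answer literally. Someone told to hold the drug may not count those days, and the English text is a translation of a French form. This stands as a limit on certainty. The result is conditional on a literal answer.

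A third is that readers will see the interruption table anyway. They will, but nothing in the protocol links it to the adherence categories.

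A reader might infer more than the documents support:

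- *That prescribed stops are reported as poor adherence.* The stop alone gives 1 or 2, which is average. It never reaches the low category.
- *That the effect holds whichever way the scale is scored.* Under the contradictory coding as written it does not, since a Yes on item 2 moves the score towards the high label and everyone in the example is low.
- *That it creates a spurious link between adverse events and adherence, or an apparent improvement over time.* Section 7.4 gives a general rationale about adherence and toxicity management, but section 9.7.3 only describes the score. Nothing states that interruptions cluster at early visits.

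**Conclusion.** The point holds in a limited form. With the coding contradiction resolved so that zero lapses means high adherence, an otherwise perfect patient who has resumed after a doctor-ordered stop in the last 14 days, and who answers item 2 literally, cannot be classed as high and falls to average. A patient still interrupted would fail item 5 as well and score 2, still average. Whether that patient counts as under treatment, and so receives the form, is not stated.

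The size is unknown. The 2.3–6.2% of forms per visit for resumed patients rests on an assumed 15–40% interruption rate within a single 91-day window. The 3.5–15.4% range further assumes that interrupted patients complete the form and that stops last 7–21 days. Interruptions spread over three years would bring the share well below 2%. The Study 200 cytopenia rates in section 7.3 are not interruption rates and do not settle it.

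**What to change.** First settle the item coding, the reversal of item 5, the code for item 8 and the cut-offs; without that no category is interpretable. Then, in the adherence part of section 9.7.3:

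- keep the description of all returned forms;
- flag forms completed during, or within 14 days after, a doctor-ordered temporary discontinuation recorded in the eCRF;
- present the adherence categories with and without the flagged forms;
- state whether a temporarily interrupted patient counts as under treatment for completing the form.

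Showing both versions is better than dropping the flagged forms from the main description, which would selectively remove patients with toxicity and discard their answers to the other items.

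The cost is one extra table with small cell counts. Section 9.7.3 already requires the reason for and cumulative duration of interruptions, but the protocol does not say that the recorded reason separates doctor-ordered from patient-initiated stops. Check that, and that the dates allow the 14-day window to be applied, before relying on the flag.

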### 9.2.1. Criteria for inclusion

Patients must satisfy all of the following criteria for inclusion in order to be eligible.

- Male or female patient 18 years of age or older;
- Patient with BCR-ABL Philadelphia chromosome positive or negative CML, in chronic, accelerated or blast phase;
- Patient resistant or intolerant to previous therapy with TKI for CP, AP or CB CML other than bosutinib;
- Patient initiating treatment with bosutinib for treatment of CP, AP or BP phase Ph+ / - CML at the end of the inclusion visit or during the one month prior to it;
- Patient who has been informed that a method of contraception must be used if a risk of pregnancy exists.
- Patients who have been informed about the study and who signed the informed consent form.

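### Item 3 of the Morisky form asks about 'ever' and the form does not name bosutinib, so one past episode can recur in every later on-treatment adherence score

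*Protocol*

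**What the plan says.** Adherence to bosutinib, measured by the Morisky self-questionnaire, is a secondary objective (Protocol 8.2). Section 9.3 lists the variable as "Compliance with treatment with bosutinib (Morisky Questionnaire" and gives the follow-up visits as its source. Under section 9.4.1 and Table 4 the form is completed at every follow-up visit, M3 to M36, but only while the patient is taking bosutinib; it stops at the long-term follow-up visits.

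On analysis, section 9.7.3 says: "The score will be described continuously and categorically", at each measurement time. Items are coded Yes = 0 and No = 1 and added. The categories are 0 for high adherence, 1 to 2 for average, and 3 or more for low. Section 9.4.1.5 uses the same item coding and describes Yes as the sign of poor compliance.

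The form itself (Annex 3.3) is headed "Questionnaire in relation to your treatment". It does not mention bosutinib and gives no general recall period. Two items carry their own window. Item 2 reads in part: "By thinking about the last two weeks, have there been any days when you did not take your treatment". Item 5 asks about yesterday. Item 3 has none: "Has it ever happened for you to reduce the dose or to discontinue taking your treatment without telling your doctor".

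Every participant has been on another drug of the class. The inclusion criterion in section 9.2.1 reads: "Patient resistant or intolerant to previous therapy with TKI for CP, AP or CB CML other than bosutinib".

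**The concern.** A score described at each visit should be able to move both ways: down when a patient lapses, up when the patient resumes. An item that asks whether something has ever happened cannot do that if it is answered literally. Once the truthful answer is Yes it stays Yes, however well the patient takes bosutinib afterwards. The total then mixes recent conduct (items 2 and 5), habitual conduct (items 1, 4, 6, 7 and 8) and history without limit (item 3).

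The missing drug name adds a second ambiguity. These patients were resistant or intolerant to an earlier tyrosine kinase inhibitor, and item 3 asks about cutting or stopping treatment because it makes the patient feel worse. A patient could have such an episode on the earlier drug in mind. What is at stake is whether the adherence time course can be read as one.

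**Working it through.** The protocol states no figure on this point, so there is none to reproduce. The check compares the wording with the intended use and then scores one patient under the possible rules.

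**Wording against use**

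| Element | Intended use (8.2, 9.3, 9.7.3) | Form (Annex 3.3) |
|---|---|---|
| Drug | Bosutinib | Not named |
| Time | Each measurement time | No general period; windows only in items 2 and 5 |
| Item 3 | Part of the score at each visit | Ever, without limit |

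For contrast, the quality-of-life form in Annex 3.4 sets a seven-day period for all its questions.

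**Number of administrations.** Table 4 marks M3, M6, and so on to M36: 36 / 3 = 12, for a patient who stays on bosutinib throughout.

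**Effect of one Yes on item 3.** Take a patient who is otherwise fully adherent: No to items 1, 2, 4, 6 and 7, and Yes to item 5 (took the treatment yesterday). Item 8 is held at 0 because its points are not stated.

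- *Section 9.7.3 as written (Yes = 0, No = 1).* With item 3 = No: six No answers give 6, category low. With item 3 = Yes: five No answers give 5, category low. The Yes moves the score towards the end labelled high adherence.
- *Count of non-adherent answers, with item 5 reversed.* This is the direction that the category cut-offs imply, but the protocol does not state it. With item 3 = No: 0, category high. With item 3 = Yes: 1, category average. A patient already at 2 (average) moves to 3 (low).

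On the second rule, a lasting Yes rules out the high category at every later on-treatment visit. Under either rule item 3 stays fixed; the rule decides only which way it pulls the total.

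**Illustration of the mechanism, on assumed rates.** Suppose a constant share r of patients newly has such an episode on bosutinib in each 3-month interval, intervals are independent, everyone stays on treatment, and everyone answers literally. The share answering Yes after k visits is 1 − (1 − r)^k. For k = 12:

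- r = 0.02: 1 − 0.98^12 = 0.215
- r = 0.05: 1 − 0.95^12 = 0.460
- r = 0.10: 1 − 0.90^12 = 0.718

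The rate of new episodes is flat in each case, yet the Yes share rises from 2%, 5% or 10% at M3 to about 22%, 46% or 72% at M36. No carry-over from an earlier drug is needed. The rates have no source in the protocol, and patients who stop bosutinib also stop completing the form, so these figures show how the item behaves and do not estimate its effect here.

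**The case against.** The strongest reply is that the setting supplies what the heading omits. Only patients on bosutinib receive the form, they complete it on site at the visit (9.4.1), and patients on another treatment are not included (9.2.2). In that setting, treatment in the singular most naturally means the current drug. Section 9.4.1.5 calls the scale generic, standardized and validated, and a generic scale would not name a drug. The English text is also visibly a rough translation, so how strictly the French item says 'ever' cannot be judged from it.

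Much of this stands. A reader might infer that conduct on the earlier drug is in fact being counted as non-adherence to bosutinib. The protocol does not show that: nothing tells the patient to include it, just as nothing tells the patient to leave it out. Section 9.4 does list a compliance questionnaire at inclusion, when bosutinib may not yet have started, but section 9.4.1 and Table 4 point against an M0 form. Carry-over is possible, not established. What the reply does not answer is the missing window: an unreported stop on bosutinib itself is enough to fix item 3 at Yes.

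A reader might also infer that one old episode produces a fresh adverse event report at each visit, because section 9.4.1.5 gives as a cue "if the patient has ticked YES to questions" 3 or 6. That goes too far. The rule covers events that the participating doctor identifies, so judgement stands between the tick and the report. Section 11.3 starts the reporting period at the first bosutinib dose, or at consent if the patient is already exposed.

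**Conclusion.** The point holds and is minor. As printed, item 3 cannot show a return to adherence, and the form does not tie the answers to bosutinib, while section 9.7.3 describes the total visit by visit as adherence to that drug. It concerns one item of eight, in a descriptive secondary objective without a hypothesis, and only patients with such an episode, at visits while they are on bosutinib.

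Two things limit the conclusion. The size is unknown: the protocol gives no frequency for such episodes on bosutinib or on earlier drugs. The direction is open too. A reader might infer that adherence is understated, and increasingly so over the three years. That follows only if Yes counts against the patient in the total, as section 9.4.1.5 intends. Section 9.7.3 codes Yes as 0 and then labels 0 high adherence, so the written rule pulls the other way. That contradiction comes first and is the larger defect, but resolving it would not give item 3 a window.

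**What to change.** 1. Reconcile the scoring in section 9.7.3 with section 9.4.1.5, so that the direction of the total and its categories agree.
2. Leave all eight items and the windows printed in items 2 and 5 unchanged. Add the words 'with bosutinib' to the form's heading.
3. In section 9.7.3, report item 3 separately as a cumulative item: the share of patients who have given a first Yes by each visit.
4. In the same section, add a sensitivity description of the score at each visit without item 3, next to the full score. This also serves the forms already collected.

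A general instruction to answer for the time since the last visit is not advised: it would clash with the windows in items 2 and 5 and would alter a questionnaire described as validated. The adverse event reporting rule should stay as it is.

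The cost is one extra table and a slight change of heading, so that early and late forms differ a little. The score without item 3 is not itself the validated scale and should be labelled as a sensitivity description only.

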**ANNEX 3.4: FACT-leu questionnaire 4th version**

You will find below a list of comments that other persons with the same illness as yours have considered important. **Please indicate your response by circling a single figure per line and by taking into account the last 7 days.**

	PHYSICAL WELL-BEING	Not at all	A little	Moderately	Much	Enormously
GP1	I lack energy.....	0	1	2	3	4
GP2	I have nausea.....	0	1	2	3	4
GP3	Because of my physical condition, I have difficulty in responding to the needs of my family	0	1	2	3	4
GP4	I have pain.....	0	1	2	3	4
GP5	I am bothered by the side effects of treatment .....	0	1	2	3	4
GP6	I feel ill.....	0	1	2	3	4
GP7	I must spend time lying down.....	0	1	2	3	4

	SOCIAL/FAMILIAL WELL-BEING	Not at all	A little	Moderately	Much	Enormously
GS1	I feel close to my friends .....	0	1	2	3	4
GS2	My family provides me with moral support .....	0	1	2	3	4
GS3	My friends support me.....	0	1	2	3	4
GS4	My family has accepted my illness.....	0	1	2	3	4
GS5	I am satisfied by communication with my family on subject of my illness .....	0	1	2	3	4
GS6	I feel close to my partner (or the person who is my principal caregiver).....	0	1	2	3	4
Q1	Whatever your degree of sexual activity at this time, please respond to the following question. If you prefer to not respond to it, tick this box and go on to the next section.					
GS7	I am satisfied with my sex life.....	0	1	2	3	4

	EMOTIONAL WELL-BEING	Not at all	A little	Moderately	Much	Enormously
GE1	I feel sad.....	0	1	2	3	4
GE2	I am satisfied with the manner in which I face my illness	0	1	2	3	4
GE3	I am losing hope in the fight against my illness .....	0	1	2	3	4
GE4	I feel nervous 0	0	1	2	3	4
GE5	I am concerned by the thought of dying 0	0	1	2	3	4
GE6	I am concerned by the thought that my health condition may worsen.....	0	1	2	3	4

	FUNCTIONAL WELL-BEING	Not at all	A little	Moderately	Much	Enormously
GF1	I am able to work (including housework).....	0	1	2	3	4
GF2	My work (including housework) gives me satisfaction..	0	1	2	3	4
GF3	I am able to obtain benefit from life .....	0	1	2	3	4
GF4	I have accepted my illness .....	0	1	2	3	4
GF5	I sleep well .....	0	1	2	3	4
GF6	I appreciate my usual leisure .....	0	1	2	3	4
GF7	I am satisfied with my current quality of life .....	0	1	2	3	4

	OTHER SUBJECTS OF CONCERN	Not at all	A little	Modera tely	Much	Enormo usly
BRM3	I am bothered by fever	0	1	2	3	4
P2	Some parts of my body are painful	0	1	2	3	4
BRM2	I am bothered by chills	0	1	2	3	4
ES3	I have night sweats	0	1	2	3	4
LEU1	I am bothered by lumps or swelling in certain parts of my body (for example, neck, armpits or groin)	0	1	2	3	4
TH1	I bleed easily	0	1	2	3	4
TH2	I easily bruise	0	1	2	3	4
HI12	I feel general weakness	0	1	2	3	4
BMT6	I tire easily	0	1	2	3	4
C2	I lose weight	0	1	2	3	4
C6	I have a good appetite	0	1	2	3	4
An7	I am able to perform my usual activities	0	1	2	3	4

N3	I am concerned by the thought of contracting an infection.....	0	1	2	3	4
LEU 5	I experience uncertainty regarding my future health....	0	1	2	3	4
LEU 6	I am concerned about the idea of the occurrence of new symptoms of my illness .....	0	1	2	3	4
BRM 9	Emotionally, I experience highs and lows.....	0	1	2	3	4
LEU 7	I feel isolated from others because of my illness or because of my treatment.....	0	1	2	3	4

